[name]
[name]

VERSION: 1.10

ISSUE DATE: 26 DECEMBER 2013

PRIMARY INVESTIGATOR: [name]
DIRECTOR, CARDIOVASCULAR RESEARCH AND ADVANCED
EDUCATION
MEDSTAR HEART INSTITUTE
[name]
[name]
[contact]
[contact]

CLINICALTRIALS.GOV: NCT02033694

LRP SYNOPSIS

Study Name: Lipid-rich Plaque (LRP) Study

Primary Purpose of the Study:
 
The Lipid-rich Plaque Study will determine the relationship in patients undergoing IVUS-NIRS (near-infrared spectroscopy) imaging between lipid-rich plaque detected by intracoronary NIRS at non-stenotic sites and subsequent coronary events from new culprit lesions at both the patient level (vulnerable patients) and the segment level (vulnerable plaques).

Name of Device for Detection of Lipid-rich Plaque:
 
The TVC Imaging system, which performs IVUS-NIRS imaging in a single pullback, is manufactured by InfraReDx, Inc. of Burlington, MA, USA. The TVC system is FDA approved for use to detect lipid core plaque and lipid core burden index, and to perform IVUS imaging for routine clinical purposes. NIRS has been used in over 5,000 patients world-wide in over 100 hospitals.

Study Leadership:
 
Principal Investigator, Worldwide: [name], Medstar Heart Institute, Washington, DC, USA Principal Investigator, Japan: [name], Wakayama, Japan Co-Principal Investigator, Japan: [name], Osaka, Japan Principal Investigator, Europe: [name] [name], London, England Principal Investigator, Korea: [name], Seoul, Korea Project Manager: [name], Medstar Heart Institute, Washington, DC, USA

Sponsor: Infraredx, Inc. Burlington, MA, USA Statistical Consultant: [name], Harvard School of Public Health, Boston, MA

Funding company:
 
InfraReDx, Inc. Burlington, MA, USA Chief Medical Officer, [name] Project Coordinator, [name]

Study centers:
 
Up to 100 sites world-wide (except in Scandinavia where PROSPECT II is being conducted with TVC).

Planned study period:
 
2014-2018


Background:
 
The LRP Study is being initiated because of the success of both IVUS and NIRS in identifying vulnerable patients and vulnerable plaques. The PROSPECT Study and 4 additional IVUS studies have shown that plaques that occupy more than 70% of the area of the external elastic membrane (>70% plaque burden) as measured by IVUS have an increased likelihood of causing a coronary event. (Madder et al, JIC Supplement, 2013)
 
While the IVUS success is based on size of a plaque, the novel NIRS system has shown promise based on analysis of plaque composition. The distinctive signature of a cholesterol plaque has now been found at the site of STEMI culprit lesions (Madder et al, JACC Interventions 2013). In addition patients with increased cholesterol in a non-culprit artery have been shown to have a 4-fold multivariate increase in the risk of a coronary event over the subsequent year. (Oemrawsingh et al, Journal of the American College of Cardiology, in press, 2014).

Objectives:

The Lipid-rich Plaque Study will be performed in patients undergoing IVUS-NIRS imaging (the index procedure) in whom a TVC catheter will be purchased and used for routine clinical indications. The study will test the ability of multi-vessel NIRS scanning for LRP in coronary segments without significant stenoses as a means to predict new coronary events arising from a new culprit lesion (a non-index culprit lesion). Analyses will be performed at both the patient level (vulnerable patients) and the segment level (vulnerable plaques).

If and when it is determined that vulnerable patients and vulnerable plaques can be detected by multi-vessel NIRS scanning, the study will transition from a detection study to a treatment study. This will require a separate protocol with separate IRB approval.

Methodology:

The LRP Study is a multicenter, prospective registry of patients with stable ischemic heart disease or a stabilized acute coronary syndrome (ACS) examined with angiography and IVUS-NIRS imaging for one or more suspected culprit lesions. After successful PCI of all angiographically flow-limiting lesions, intravascular imaging with the combined IVUS-NIRS catheter will be performed in all three coronary arteries if possible. Successful imaging of at least two vessels and a total of 50 mm of coronary artery is required for enrollment. All enrolled patients with a large LRP as detected by NIRS will be contacted at 2,6,12 and 24 months by phone to determine if a new coronary event has occurred. A randomly selected half of the patients with a small, or no, LRP will receive an identical follow-up. The origin of any new event will be determined by the follow-up angiography performed for clinical indications. The location of new culprit lesions will be identified and compared to the baseline NIRS findings in a central angiographic and NIRS-IVUS core laboratory located at MedStar.

Estimated number of subjects:

The goal is to enroll 9000 patients in the LRP Study. On the basis of the findings in the PROSPECT Study and the NIRS STEMI findings it is not expected that all 9,000 will be required to demonstrate successful prediction of coronary events with IVUS-NIRS imaging. If and when the goal of prediction is reached, the study will transition to a study of systemic and/or regional therapy of vulnerable patients and plaques.

Patient Enrollment and Procedure Overview:

Patients with stable ischemic heart disease or an ACS and planned coronary angiography in whom IVUS-NIRS imaging is likely to be performed will be asked to provide their consent for participation in the study. Angiography and PCI will be performed as clinically indicated. Unblinded NIRS IVUS imaging will be performed in the vessel, or vessels, containing a single or multiple suspected culprit lesions. Imaging for research purposes will begin in non-culprit vessels after all clinically indicated PCI has been performed. If a staged procedure is required to achieve revascularization of all lesions detected by angiography, the patient is not enrolled until after the staged procedure is successful and uncomplicated.

Imaging results in an artery not suspected to be a culprit will be blinded for NIRS, but not for IVUS.

The imaging goal, which may not be attainable in all cases, is to obtain IVUS-NIRS imaging from all 3 major coronary arteries.

The patient is formally enrolled in LRP after successful and uncomplicated PCI, and after the physician investigator determines that a total of at least 50 mm of IVUS-NIRS imaging data has been obtained from at least 2 major coronary arteries

Inclusion Criteria:**General Inclusion Criteria**

1. Subjects presenting for coronary angiography in whom IVUS imaging is likely to be performed for clinical purposes.
2. Greater than 18 years of age.
3. Clinical presenting symptoms meeting one of the three criteria below:
 1. Subjects presenting with an acute coronary syndrome (ACS) including at least one of the following:
 - a) Elevated cardiac biomarkers with CK-MB or troponin greater than upper limits of normal;
 - b) ST depression or ST elevation >1mm in 2 or more contiguous leads in the absence of LVH, paced rhythm, BBB or early repolarization;
 - c) A stabilized patient 24 to 72 hours post STEMI;
 2. Unstable angina pectoris;
 3. Stable angina pectoris and/or a positive functional study with evidence of ischemia.

Angiographic Inclusion Criteria

4. At least one Suspected Index Culprit Lesion requiring imaging with IVUS and/or NIRS for clinical indications.
5. At least two native epicardial coronary arteries (which may include the Suspected Index Culprit Artery) eligible for imaging with NIRS-IVUS.

Total IVUS/NIRS Imaging Inclusion Criterion

6. A minimum of a total 50 mm of coronary artery not involved in a prior or Index Procedure PCI (including the 5mm borders on either edge of the site receiving PCI) must be scanned. This 50mm total length may include contributions from the Suspected Index Culprit Arteries and from Index Non-Culprit Arteries. This total length must include contributions from two or more native imaged arteries.

Exclusion Criteria

1. Unstable patients (STEMI within the prior 24 hours; cardiogenic shock, hypotension needing inotropes, hypoxia needing intubation, and IABP) and patients that had a procedural complication (coronary dissection, perforation or a complication that would necessitate immediate-unplanned revascularization) during index PCI procedure.
2. History of CABG or planned CABG within 6 months following NIRS-IVUS imaging.
3. Patient has additional lesion(s) that needs a staged PCI.
4. Subject life expectancy is less than 2 years at time of index catheterization.
5. Subject with ejection fraction (EF) <30%.
6. Subject pacemaker dependent/paced rhythm.
7. Subject pregnant and lactating.
8. Any other factor that the investigator feels would put the patient at increased risk or otherwise make the patient unsuitable for participation in the protocol

9. Patients undergoing performance of PCI in all three major vessels during the index PCI.

Study follow-up:

All enrolled patients with a large LRP (Maximum Lipid Core Burden Index > 250 in 4 mm) will be contacted by phone by the study coordinator for each clinical site at 2, 6, 12 and 24 months to determine if a new coronary event has occurred. A randomly selected half of the patients with a small, or no LRP (Max 4mm LCBI < 250) will receive an identical follow-up. The determination of the need for follow-up will be made by the NIRS core lab after unblinding of the NIRS data and communicated to the clinical site prior to the 2 month follow-up.

The origin of any new event will be determined by the follow-up angiography performed for clinical indications. Clinical and imaging data for any follow-up event will be sent to the central angiographic and IVUS/NIRS core laboratory located at MedStar. The location of new culprit lesions will be identified by a clinical events committee (blinded to the baseline NIRS results), and compared to the baseline NIRS findings by the core laboratory.

Endpoints:

The primary outcome variable is Non-Index Culprit Lesion related Major Adverse Cardiac Events (NC-MACE) defined as the composite of:

- cardiac death,
- cardiac arrest,
- non-fatal myocardial infarction (MI),
- acute coronary syndrome,
- revascularization by CABG or PCI,
- rehospitalization for progressive angina, adjudicated to a non- index culprit lesion secondary to significant fixed, non-reversible (not-spasm related) lesion progression of more than 20% from the baseline study (confirmed by either serial angiography or by necropsy).

Statistical methods:

The study will test two primary hypotheses:

1)The Vulnerable Patient Hypothesis -- During a 24-month follow-up after IVUS-NIRS imaging, there will be an association between the baseline value of max 4mm LCBI (over all coronary artery segments included in the analysis) and the incidence of non- index culprit MACE events.

1 DEFINITIONS

Major Adverse Cardiac Event (MACE) is

- cardiac death,
- cardiac arrest,
- non-fatal myocardial infarction (MI),
- acute coronary syndrome,
- revascularization by CABG or PCI,
- rehospitalization for progressive angina, adjudicated to a non-index-culprit lesion secondary to significant fixed, non-reversible (not-spasm related) lesion progression of more than 20% from the baseline study (confirmed by either serial angiography or by necropsy).

Follow-up Culprit Lesion -A lesion causing a Major Adverse Cardiac Event during the follow up period.

Non-Culprit Major Adverse Cardiac Event (NC-MACE) -A MACE that occurs due to a Follow-up Culprit Lesion not located at a site that underwent PCI at the time of Index Procedure.

PCI-related Major Adverse Cardiac Event (PCI-MACE) -As MACE that occurs due to a Follow up Culprit Lesion where the site of the Follow up Culprit Lesion is one in which PCI was performed at the index procedure.

Suspected Index Culprit Lesion is a lesion or multiple lesions requiring clinically necessary NIRS-IVUS interrogation at the time of the index procedure.

Index Suspected Culprit Artery -An artery or arteries that contains at least one Suspected Culprit Lesion at the time of the index procedure.

Index Culprit Lesion- A lesion considered to be responsible for the presenting symptoms at the time of the index procedure.

Index Non Culprit Artery - An artery that contains no culprit lesions at the time of the index procedure.

Large LRP - At least one 4 mm length of artery with a LCBI ≥ 250 as assessed by IVUS-NIRS imaging

Major Epicardial Arteries -The left anterior descending, left circumflex, and right coronary arteries and the branches associated with each.

Index procedure -The catheterization procedure that qualified the patient to be screened for this study.

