2.1.2 PRIMARY HYPOTHESES

Two hypotheses will be tested for plaques at non-stenotic sites that have not undergone PCI:

First, patients with increased max 4mm LCBI in all scanned arteries are more likely to experience NC-MACE than those without increased max 4mm LCBI (the vulnerable patient hypothesis);

Second, coronary artery segments (defined as the proximal, mid, and distal segments of the major epicardial arteries,) with increased max 4mm LCBI (within the segment) are more likely than segments without increased max 4mm LCBI to cause NC-MACE (the vulnerable plaque hypothesis).

The portion of the coronary artery or arteries to be studied will meet all of the following criteria:

- The portion of the coronary artery does not contain a flow-limiting stenosis, defined as > 50% diameter stenosis by visual angiographic estimate;
- The portion of the coronary artery has not undergone PCI in the past, and PCI is not performed at the index event or planned in a staged procedure. The length of artery excluded from the study because of PCI includes a 5mm border on either side of the intervened segment.

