3 ENDPOINTS

3.1 PRIMARY BASELINE MEASUREMENTS AND ENDPOINTS

For the Test of the Vulnerable Patient Hypothesis

The primary baseline measurement will be the maximum LCBI in 4 mm (max 4mm LCBI) over all scanned portions of the coronary arteries. The portion of artery to be scanned will exclude sites in which PCI has been performed in the past or will be performed in the index procedure (also excluding 5 mm borders of any site that underwent PCI).

The primary endpoint for the test of the vulnerable patient hypothesis will be the incidence of NC-MACE within 24 months.

The primary hypothesis is that risk of NC-MACE will be positively associated with max 4 mm LCBI measured as a continuous variable. The exposure-response relationship will also be evaluated for max 4 mm LCBI expressed as a binary variable above and below varying thresholds. It is hypothesized that increasing levels of max 4mm LCBI will identify increasing levels of risk for the patient of experiencing NC-MACE within 24 months following the artery imaging.

For the Test of the Vulnerable Plaque Hypothesis

The primary baseline measurement will be the maximum 4 mm LCBI detected in each proximal, mid, or distal segment of coronary artery scanned. The portion of artery to be scanned will exclude sites in which PCI has been performed in the past or will be performed in the index procedure (including 5 mm borders of any site that underwent PCI).

The primary endpoint for the test of the vulnerable plaque hypothesis will be the incidence of NC-MACE within 24 months.

The exposure-response function will be calculated for varying levels of max 4mm LCBI for each coronary artery segment. It is hypothesized that increased levels of max 4 mm LCBI in a coronary artery segment will identify increased levels of risk for that segment of causing NC-MACE within 24 months following the artery imaging.

FOLLOW-UP

All patients with a large LRP (defined as at least one 4mm segment with a max LCBI \geq 250 as assessed by IVUS-NIRS imaging) will be followed for 24 months to determine the occurrence of NC-MACE. Patients without at least one large LRP will be randomly allocated in a 1:1 ratio to 24 month follow-up or no follow-up.

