4.1.1 INCLUSION CRITERIA

Subjects must meet all of the following inclusion criteria prior to enrollment in the study:

General Inclusion Criteria

1. Subjects presenting for coronary angiography in whom IVUS imaging is likely to be performed for clinical purposes.
2. Greater than 18 years of age.
3. Clinical presenting symptoms meeting one of the three criteria below:
 1. Subjects presenting with ACS defined as at least one of the following:
 - a) Elevated cardiac biomarkers with CK-MB or troponin greater than upper limits of normal range;
 - b) ST depression or ST elevation >1mm in 2 or more contiguous leads in the absence of LVH, paced rhythm, BBB or early repolarization;
 - c) A stabilized patient 24 to 72 hours post STEMI;
 2. Unstable angina pectoris;
 3. Stable Angina Pectoris and/or a positive functional study with evidence of ischemia.

Angiographic Inclusion Criteria

4. At least one Suspected Index Culprit Lesion requiring imaging with IVUS and/or NIRS for clinical indications.

5. At least two native epicardial coronary arteries (including the Suspected Index Culprit Artery) eligible for imaging with NIRS-IVUS

Total IVUS/NIRS Imaging Inclusion Criterion

6. A minimum of a total 50 mm of coronary artery not involved in a prior or Index Procedure PCI (including the 5mm borders on either edge of the site receiving PCI) must be scanned. This 50mm total length may include contributions from the Suspected Index Culprit Arteries and from Index Non-Culprit Arteries. This total length must include contributions from two or more native imaged arteries.

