4.1.2 EXCLUSION CRITERIA

Subjects must meet none of the following exclusion criteria prior to enrollment:

General Exclusion Criteria

1. Unstable patients (STEMI within the prior 24 hours; cardiogenic shock, hypotension needing inotropes, hypoxia needing intubation, and IABP) and patients that had a procedural complication (coronary dissection, perforation or a complication that would necessitate immediate-unplanned revascularization) during index PCI procedure.
2. History of CABG or planned CABG within 6 months following NIRS-IVUS imaging.
3. Patient has additional lesion(s) that needs a staged PCI.
4. Subject life expectancy is less than 2 years at time of index catheterization.
5. Subject with ejection fraction (EF) <30%.
6. Subject pacemaker dependent/paced rhythm.
7. Subject pregnant and lactating.
8. Any other factor that the investigator feels would put the patient at increased risk or otherwise make the patient unsuitable for participation in the protocol.
9. Patients undergoing performance of PCI in all three major vessels during the index PCI.

4.2 REVIEW OF CHEMOGRAM TO DETERMINE PROTOCOL FOR FOLLOW-UP DEPENDING ON THE PRESENCE OR ABSENCE OF A LARGE LRP

At the end of the index procedure the chemogram (the NIRS findings output) data for both the Suspected Index Culprit Lesion or Lesions (unblinded) and Index Non-culprit (blinded) Arteries will be submitted to the NIRS Core Laboratory for evaluation. The Core Lab will review the chemogram to determine if a large LRP is present in an area that:

- 1) had not undergone PCI in the past,
- 2) did not undergo PCI at the time of the index procedure.

Areas that have undergone PCI (stent, balloon or other device) plus a 5 mm border on either side of the intervened area will be excluded from analysis.

A "large LRP" will be defined as a 4mm segment within the eligible area with an LCBI \geq 250.

The Large LRP Group: All patients with a large LRP will be followed with a phone inquiry at 2,6,12 and 24 months post enrollment.

The Small or No LRP Group: Of this group, 50% will be randomly assigned (in a 1:1 fashion) to be followed with a phone inquiry at 2,6,12 and 24 months post enrollment.

The follow-up status for each patient will be determined by the core lab and communicated to the site coordinator prior to the 2 month follow-up window for the call. The clinical site will remain blinded to the NIRS findings, as will the clinical events committee.

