5.1.3 ALLOCATION TO FOLLOW UP

For patients who are enrolled, the IVUS-NIRS images will be submitted to the NIRS Core Laboratory within 5 business days of collection and enrollment. The NIRS Core Lab will then assess the totality of NIRS findings, excluding locations and 10 mm borders of locations that underwent PCI, to establish the patient level max 4mm LCBI of all scanned segments. The NIRS Core Lab determination that the per patient max 4mm LCBI is below 250 will indicate that the patient will be randomized to follow-up or no follow-up. Patients with values above > or = to 250 will all receive follow-up per figure 1. The NIRS Core Lab will provide notification to the site prior to the 60 day follow up time interval to indicate to the sites which patients require follow up. The patient will be allocated as below:

- Patients with a max 4mm LCBI of all scanned segment ≥ 250 will be followed for a 2 year period as described in section 5.1.3.
- Patients with a max 4mm LCBI of all scanned segment < 250 will be randomized to follow up or no follow up beyond hospital discharge. Patients randomized (in a 1:1 fashion) to follow up will be followed for a 2 year period as described in section 5.1.3. The allocation will occur within the electronic case report form system and will take into consideration the site and have a set block size to help mitigate unequal allocation by site. Patient allocated to no follow up beyond hospital discharge will only have data collected through hospitalization within the electronic case report form.

The NIRS findings from the Index Non-culprit Artery details including the Core Lab determined patient-level max 4mm LCBI will be blinded to the clinical site.

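### The PCI border for follow-up allocation is stated two ways (5 mm and 10 mm), and NC-MACE as defined can count events at treated sites that the primary hypotheses and the LCBI exposure leave out

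*Combined protocol and SAP*

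**What the plan says.** **Outcome.** Section 1 defines NC-MACE as "A MACE that occurs due to a Follow-up Culprit Lesion not located at a site that underwent PCI at the time of Index Procedure". Its mirror image, PCI-MACE, applies where "the site of the Follow up Culprit Lesion is one in which PCI was performed at the index procedure". Neither definition mentions earlier PCI or a border.

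**Hypotheses and exposure.** Section 2.1.2 opens with "Two hypotheses will be tested for plaques at non-stenotic sites that have not undergone PCI" and goes on to rule out past, index and staged PCI with a 5 mm border. Section 3.1 has the scanned length "exclude sites in which PCI has been performed in the past or will be performed in the index procedure". For the patient-level measurement it then adds a margin, in the words "also excluding 5 mm borders of any site that underwent PCI".

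**Eligibility.** Section 4.1.2 excludes a history of CABG but not of PCI. Inclusion criterion 6 in Section 4.1.1 allows for earlier PCI: the 50 mm minimum refers to length "not involved in a prior or Index Procedure PCI (including the 5mm borders on either edge of the site receiving PCI) must be scanned".

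**Allocation.** Section 4.2, on the core lab's review to decide follow-up, says that treated areas "plus a 5 mm border on either side of the intervened area will be excluded from analysis". Section 5.1.3, on the same decision, has the core lab set the patient-level value "excluding locations and 10 mm borders of locations that underwent PCI". Patients at or above 250 are all followed; those below are randomised 1:1 to follow-up or none.

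**The concern.** There are two separate problems.

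**(a) Border.** The allocation rule contradicts itself. If 10 mm is applied, a patient whose only 4 mm window at or above 250 lies 5–10 mm from a PCI site is large-LRP for the exposure in Section 3.1 but goes into the half-sampled group. Section 6.1 calls for weighted estimation of the ROC curve and the net reclassification improvement (NRI). Those weights are wrong for this patient if they follow the analysed LCBI and not the rule used at allocation.

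**(b) Endpoint scope.** For the patient-level hypothesis (H1), an event can be counted from artery that the hypothesis and the exposure both set aside. The hazard ratio per 100 LCBI units would then mix events from untreated plaque with events at treated sites. For the segment-level hypothesis (H2) the gap is one of wording: the outcome description in Section 6.1 does not repeat the exclusion that other sections apply to the segments.

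**Working it through.** **Border: the texts side by side.** A 5 mm border appears in synopsis inclusion criterion 6 and Sections 2.1.2, 3.1, 4.1.1, 4.2, 5, 5.1.2.1 and 5.1.6. A 10 mm border appears only in Section 5.1.3. Sections 4.2 and 5.1.3 govern the same core-lab decision.

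The two rules differ by 10 − 5 = 5 mm at each edge, which can hold a whole 4 mm window. A patient can therefore be at or above 250 under one rule and below 250 under the other.

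**Border: illustration.** Inputs from Section 6.2 are 3,000 large-LRP patients with 300 expected events (10%), and 720 events overall. The share m of large-LRP patients who qualify only in the 5–10 mm band is not in the documents, so m = 2, 5 and 10% is an assumption.

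- Mis-allocated if 10 mm is applied: 3,000 × m = 60, 150, 300.
- Not followed (half): 30, 75, 150.
- Large-LRP events not observed, e, at 10%: 3, 7.5, 15.
- Sensitivity at 250 with correct weights: 300/720 = 41.7%.
- With weights that follow the analysed LCBI, (300 − e)/(720 − e): 297/717 = 41.4%, 292.5/712.5 = 41.1%, 285/705 = 40.4%.

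**Endpoint: reproducing the plan's power.** For a continuous covariate in a Cox model, power = Φ(√D × SD × ln HR − 1.96). Here D is the number of events, SD = 1 (in units of 100 LCBI) and alpha is the plan's two-sided 0.05. At 5% incidence D = 6,000 × 0.05 = 300, and ln 1.18 = 0.1655. This gives Φ(17.32 × 0.1655 − 1.96) = 0.818, against 0.82 in Table 2. All fifteen cells of Table 2 agree to within 0.01.

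**Endpoint: illustration.** Let f be the share of counted events at earlier-PCI sites or in PCI borders. It is not in the documents; f = 5 and 10% is an assumption. If those events carry hazard ratio HR2, the pooled log hazard ratio is approximately (1 − f) × ln 1.18 + f × ln HR2. If they are excluded, D becomes D × (1 − f) and the hazard ratio stays 1.18.

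| Case, HR 1.18 | f = 5% | f = 10% |
|---|---|---|
| D = 300, counted, unrelated to LCBI (HR2 = 1): pooled HR | 1.170 | 1.161 |
| D = 300, same case: power | 0.777 | 0.732 |
| D = 300, counted, same HR: power | 0.818 | 0.818 |
| D = 300, excluded: power | 0.798 | 0.776 |
| D = 480 (8% row, base 0.952), counted, unrelated: power | 0.931 | 0.904 |
| D = 480, excluded: power | 0.942 | 0.931 |

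If HR2 exceeds 1.18, the pooled hazard ratio rises. The sign of the bias therefore depends on a quantity the documents do not give.

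**The case against.** **On the border.** A reader might infer that allocation is done at 10 mm and that patients will be misclassified. The documents do not show that. Section 4.2 sets the same decision at 5 mm, and 10 mm might mean two 5 mm edges added together. What stands is that the rule is stated twice and differently, and that misallocation follows under one reading. Nor does the conflict carry over to the weighting of the primary tests: Section 6.1 asks for weights in the ROC and NRI analyses and does not describe the Cox tests as weighted.

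**On H1.** A reader might infer that the primary hazard ratio is diluted. That does not follow, because the direction is unknown. A broader outcome may also be deliberate. H1 treats LCBI as a marker of patient risk, and the synopsis objectives equate a new culprit with a non-index culprit lesion. The first bullet of Section 3.3 pairs a PCI-free exposure with plain MACE. This is a fair defence of the broad endpoint, but it leaves Section 2.1.2 scoping both hypotheses to untreated sites, so one text still has to change.

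**On completeness.** Aligning the PCI sites does not make outcome and exposure coincide. Events from an unscanned third vessel, from length beyond the pullback, or from portions with more than 50% stenosis would still count for H1. That objection stands.

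**On H2.** A reader might infer that the segment analysis is compromised. Section 5.1.6 removes past and index PCI with 5 mm from the study segments, and the 30 mm and 10 mm tertiary analyses in Section 3.4 also exclude treated sites and borders. Only the cross-reference is missing.

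**Conclusion.** The concern holds in two limited parts, and both are worth settling before patients are allocated.

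(a) Sections 4.2 and 5.1.3 conflict on the border. If 10 mm is applied as a per-edge distance, some analysed large-LRP patients are followed with probability 0.5 instead of 1. On assumed shares of 2–10%, sensitivity at 250 would read 41.4–40.4% instead of 41.7%. That is small, and it rests entirely on the assumed share and on weights that follow the analysed LCBI.

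(b) The literal NC-MACE definition is wider than the scope of Section 2.1.2 and the exposure of Section 3.1. It could admit old-stent and stent-edge events to the H1 endpoint. Their number, and the direction of any bias, cannot be derived from the documents. The reason to change is agreement between hypothesis, exposure and outcome. Power is not the reason: at the 8% event rate it stays above 0.90 in every case shown.

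The H2 part is a minor wording item.

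**What to change.** 1. Reconcile Sections 4.2 and 5.1.3 to the single border used for the exposure in Section 3.1. Base sampling weights on the allocation rule actually applied to each patient.
2. In Section 1, and wherever the endpoint is restated (synopsis, 2.1.1, 3.1), define primary NC-MACE to exclude culprit lesions at any past or index PCI site and its border. Widen PCI-MACE to hold those events. Carry the same exclusion into the H2 outcome in Section 6.1.
3. Keep the present broader definition as a sensitivity analysis, and report how many events change class.
4. Classify events through the existing route in the synopsis: the clinical events committee locates the culprit and the core lab compares it with baseline. Do this step without LCBI values. The committee's blinding in Section 10.2 covers index IVUS-NIRS findings, not where PCI was done, so it is no obstacle.
5. Section 5.1.4 locates culprits only where possible, so prespecify a rule for unlocated ones. They should not be dropped from the primary endpoint by default, since they may include deaths or arrests without angiography or autopsy. Dropping them would also cost power: if 10% of 300 events were unlocated (an assumption), D = 300 × 0.9 × (1 − f) = 256.5 or 243, and power would be 0.755 or 0.732 at f = 5 or 10%.
6. State that unscanned vessel, length beyond the pullback and stenotic portions remain outside the exposure but inside the H1 outcome, and whether that is intended.

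**Cost.** Wording changes plus a location check for each adjudicated event. There will be slightly fewer primary events: if the removed 5–10% carry the same hazard ratio, power falls from 0.82 to 0.80–0.78 with 300 events, and from 0.95 to 0.94–0.93 with 480.
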